**The Effect of Virtual Reality on Pain,
Physical Function, and Health-Related
Quality of Life in Children with
Sickle Cell Disease: A Randomized
Controlled Trial**

NCT05952817

STUDY PROTOCOL

May 2025

Title: The effect of virtual reality on pain, physical function, and health-related quality of life in children with sickle cell disease: A randomized controlled trial

Significance or rationale of the study:

Virtual reality (VR) is a promising non-pharmacological pain management tool. It enhances motor function by promoting cortical reorganization and neuroplasticity. Its multimodal biofeedback engages sensory and cognitive functions, making therapy interactive, motivating, and easy to understand. With strong rehabilitation potential, VR helps patients adapt to real-world movements (Laver, 2020). Initially used for procedural pain management, VR is now expanding into chronic pain rehabilitation by encouraging engagement with difficult or avoided movements (Griffin et al., 2020). Additionally, VR offers a dynamic alternative to traditional exercises, improving adherence and outcomes. Integrating entertainment into therapy can motivate children, enhancing their physical and psychological well-being. Recently, a few studies revealed an improvement in vaso-occlusive episodes (VOE) after VR treatment (Agrawal et al., 2019). However, efficacy studies are needed to assess VR's potential benefits. Additionally, data regarding VR's efficacy on daily pain, functional mobility, and HRQOL as complementary therapy are limited

The objectives: This study aimed to assess the impact of VR on daily pain, functional mobility, and HQOL

Methods: In this single-blind Randomized Controlled Trial (RCT), 42 children aged 8 to 13 with SCD were included. They were divided into an intervention group (group I, n=21) and a control group (group II, n=21). Group I received one session of fully immersive VR for 15 minutes during hospitalization (Phase One). After discharge (Phase Two), Group I participants received fully immersive VR for 40 minutes twice /week over three weeks (six sessions) besides

medications. Yet, Group II received the prescribed drugs. Pain intensity was measured using the Numeric Rating Scale (NRS), and functional mobility was assessed with the Time UP and GO TUG test. The PedsQLTM 3.0 SCD module was used to measure the PedsQL.

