Outcomes: Investigate VR's effect on reducing daily pain in children with SCD and evaluate its impact on improving functional mobility in these children.

Examine the changes in PedsQL in children with SCD after engaging in VR experiences. 5- To evaluate the safety and satisfaction of fully immersive VR therapy in children with SCD.

Statistics: Data were analyzed using IBM SPSS Statistics Version 29.0. Descriptive statistics (means, standard deviations, frequencies, and percentages) were calculated to summarize demographic and baseline characteristics. The normality of continuous variables was assessed using the Kolmogorov-Smirnov test.

Due to the non-normal data distribution, the Mann-WhitneyU test was used to compare pain intensity scores measured by the Numeric Rating Scale (NRS) between intervention and control groups. Within-group comparisons of pre- and post-intervention scores were also conducted.

Safety outcomes from the Simulator Sickness Questionnaire were analyzed using the Chi-square test to detect any significant changes in symptoms pre- and post-intervention.

Satisfaction scores from the VR Satisfaction Likert survey were analyzed descriptively, and the Mann-Whitney U test was applied to compare satisfaction across age groups.

A significance level of $p < 0.05$ was used for all inferential statistical tests.

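### Simulator sickness before and after VR is compared in the same children with an ordinary Chi-square test, and the plan does not say which of the seven sessions are assessed or how repeats are combined

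*Combined protocol and SAP*

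**What the plan says.** The Outcomes paragraph lists as an aim: "To evaluate the safety and satisfaction of fully immersive VR therapy in children with SCD".

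Methods gives the exposure. In hospital, "Group I received one session of fully immersive VR for 15 minutes during hospitalization (Phase One"; after discharge, the same children "received fully immersive VR for 40 minutes twice /week over three weeks (six sessions". Group II receives medication only, so the exposed group is the 21 children of Group I.

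The analysis of simulator sickness is a single sentence in the Statistics paragraph, by which the questionnaire's safety outcomes were "analyzed using the Chi-square test to detect any significant changes in symptoms pre- and post-intervention". A 0.05 significance level "was used for all inferential statistical tests".

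The document does not say:
- when or how often the questionnaire is given (it is not among the measures listed in Methods);
- whether the intervention means one session, one phase or the whole course;
- how several answers from one child are combined;
- whether the 15-minute and 40-minute sessions are reported separately.

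**The concern.** There are two problems, and the first is the more certain.

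**The test does not fit the data.** A comparison of symptoms before and after VR uses two answers from the same child. The ordinary Chi-square test assumes independent observations. It looks only at the two totals and ignores which children changed, which is the information that a question about change needs. If several sessions enter, each child contributes several pairs and the independence assumption fails a second time.

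**The schedule and the summary are undefined.** The natural safety question is how many of the 21 children were made sick at any point, and whether this differs between 15 and 40 minutes. The stated contrast answers neither part. If it compares only the start of the programme with the end, a child who was sick after intermediate sessions and well after the last one counts as unaffected.

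At stake is the safety conclusion. The pain, mobility and quality-of-life comparisons are not touched.

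**Working it through.** **Exposure (from Methods).** Phase Two: 2 per week × 3 weeks = 6 sessions, which matches the stated six. Adding Phase One gives 6 + 1 = 7 per child, or 21 × 7 = 147 child-sessions. The document gives no sickness rate and no sample-size reasoning for this outcome, so all rates and correlations below are assumptions.

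**One pair per child.** Suppose 4 of 21 children have a symptom before and 10 of 21 after.
- Ordinary Chi-square, no continuity correction: pooled proportion (4 + 10)/42 = 1/3; difference 6/21 = 0.2857; variance 2 × (1/3)(2/3)/21 = 0.02116; statistic 0.2857²/0.02116 = 3.857; p = 0.0495. Pairing does not enter.
- Exact McNemar, 6 children worsen and 0 improve: 2 × (1/2)^6 = 0.031.
- Exact McNemar, 7 worsen and 1 improves: 2 × (1 + 8)/2^8 = 0.070.

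The same totals fall on either side of 0.05 according to information that the named test discards.

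**Repeated pairs, pooled.** Type I error of the Chi-square test at nominal 0.05 was simulated for 21 children × 7 sessions with no true change. The model was latent-normal with base rates of 10% to 30% and 4,000 runs per setting.

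| Correlation structure | Type I error |
|---|---|
| No clustering | about 0.05 |
| Stable child effect only (latent correlation 0.5 to 0.6) | about 0.02 |
| A child's before/after difference recurs across sessions (variance share 0.3 to 0.5) | about 0.17 to 0.25 |

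The test can therefore be too cautious or too liberal.

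**Separate test per session.** This avoids pooling but raises multiplicity: 1 − 0.95^7 = 0.30 if the seven tests are independent.

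**What a partial schedule could miss.** Assume a 5% risk at each session.
- One assessed session: 21 × 0.05 = 1.05 children expected. The chance of seeing none is 0.95^21 = 34%.
- At least once in seven, independent sessions: 1 − 0.95^7 = 30.2%, or 6.3 of 21.
- At least once in seven, within-child correlation ρ (beta-binomial with a = 0.05(1 − ρ)/ρ, b = 0.95(1 − ρ)/ρ): 1 − ∏(b + i)/(a + b + i) for i = 0 to 6.

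| ρ | Affected at least once | Of 21 | Ratio to one session |
|---|---|---|---|
| 0 | 30.2% | 6.3 | 6.0 |
| 0.1 | 24.1% | 5.1 | 4.8 |
| 0.3 | 16.9% | 3.5 | 3.4 |
| 0.5 | 12.3% | 2.6 | 2.5 |

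For per-session risks of 2% to 10% and ρ from 0.1 to 0.5, the ratio runs from about 2.3 to 5.2.

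**The case against.** The strongest reply is that much of this is missing detail rather than demonstrated error. A reader might infer that there is only one before/after contrast, so that sickness at most sessions is missed or repeats are counted as independent. The document does not support that. The questionnaire may have been given around every session, and the results may have been tested by session, tested by phase, or reduced to a worst or any-session answer per child. A by-phase analysis would also separate the two session lengths. This part of the reply stands.

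Four further inferences should also be resisted:
- **A five- to seven-fold undercount.** That size needs independent sessions. With susceptibility that differs between children, the ratio is smaller, as shown above.
- **A variance understated by 1 + 6ρ (1.6 to 4.0 for ρ of 0.1 to 0.5).** That factor is for a single pooled proportion. In a before/after contrast a stable child effect cancels, and the error has no fixed direction.
- **A known bias towards understatement** because symptoms pass quickly or affected children stop attending. The document says neither.
- **That the questionnaire can simply be added to every session.** The text is in the past tense, so collection may be finished.

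It could also be argued that Chi-square is loose wording for McNemar's test, whose large-sample statistic is referred to a chi-square distribution. If so, the plan should name it. That would settle the case of one pair per child but not that of repeated sessions.

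None of this rescues the ordinary test. Every schedule compatible with the text has before and after answers from the same children.

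**Conclusion.** The concern holds in this form: the named test, taken as the ordinary Chi-square, suits neither paired nor repeated answers under any questionnaire schedule. In addition, the plan does not define which sessions count or how a child's repeats become one result.

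On size, the paired example shows p-values moving from 0.0495 to 0.031 or 0.070, enough to change a conclusion at 0.05. Pooled sessions gave a simulated type I error between about 0.02 and 0.25. If only one session were assessed, an assumed 5% risk would show about 1 of 21 children when 12% to 30% (2.6 to 6.3 of 21) would be affected over the course, for within-child correlation from 0.5 down to 0. These figures are illustrations of what could happen. Whether sickness was in fact missed, and in which direction any test erred, cannot be told from the document.

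The change should be made because safety is a stated objective.

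**What to change.** 1. State at which sessions, and when relative to each, the questionnaire was given. Limit the safety conclusion to those sessions.
2. Replace the Chi-square test with a child-level outcome: the number of the 21 VR children with any new or worse symptom after any assessed session, with an exact 95% CI. Define new or worse in advance of the analysis. The interval also guards against over-reading a clean result: 0 of 21 has an upper limit of 1 − 0.025^(1/21) = 16%.
3. Show the 15-minute session and the 40-minute sessions separately.
4. In this count, treat a child who stopped because of symptoms as affected.
5. If a before/after test is kept, use McNemar for one pair per child. For repeated sessions use GEE or a mixed model with child as the cluster, with a small-sample correction because there are only 21 children.

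If sessions are still to come, assessing each one would close the gap, at the price of questionnaire burden. If collection is complete, items 1 to 5 can still be done with the data in hand. The cost is one extra table and possibly a narrower safety statement.

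### Satisfaction is compared between undefined age groups with a two-sample test; relating it to age in years needs no cut-point and is more powerful if the trend is roughly linear

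*Combined protocol and SAP*

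**What the plan says.** The Statistics section gives satisfaction one sentence with two parts. First, "Satisfaction scores from the VR Satisfaction Likert survey were analyzed descriptively". Second, "the Mann-Whitney U test was applied to compare satisfaction across age groups". The 0.05 significance level "was used for all inferential statistical tests", so the age comparison falls under it.

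Age appears elsewhere only as a range, under Methods: "42 children aged 8 to 13 with SCD were included". Methods also gives the allocation, "They were divided into an intervention group (group I, n=21) and a control group (group II, n=21"), and describes VR sessions for one arm only: "Group I participants received fully immersive VR for 40 minutes" in the phase after discharge.

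The objectives sentence does not mention satisfaction: "This study aimed to assess the impact of VR on daily pain, functional mobility, and HQOL". The Outcomes paragraph does: "To evaluate the safety and satisfaction of fully immersive VR therapy in children with SCD". Neither mentions age.

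**The concern.** Mann-Whitney is a two-sample test, so a single boundary somewhere between 8 and 13 is implied. Its location, the resulting group sizes and the reason for splitting are not given. A reader who sees a p-value for this comparison cannot tell which children were compared.

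Stating the boundary would cure that, but not the second problem. Splitting six years of age into two groups treats every child on one side of the line as the same age. If satisfaction rises or falls steadily with age, that wastes information in a sample that is already very small. The documents give no age hypothesis and no reason to expect a change at a particular age, which is what would favour a split.

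At stake is the reading of one secondary comparison: whether younger and older children liked the VR equally. A non-significant result could be taken as evidence that age makes no difference, when the analysis had little chance of showing one.

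**Working it through.** The plan gives no power, effect size or sample-size figure for this comparison, so there is no stated figure to reproduce.

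**Inputs from the document.** Ages 8 to 13 (six whole-year values, hence five possible two-group cuts); 21 children in the VR arm; significance level 0.05.

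**Inputs assumed.** Survey completed by the 21 VR children; ages spread evenly; one 5-point score (a normal latent variable cut at its 10th, 30th, 70th and 90th percentiles); two-sided tests; a linear latent correlation r with age of 0.3 or 0.5.

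**Step 1: information kept by a split.** For a linear trend, the relative efficiency of a split is the squared correlation between the split indicator and age, p(1−p)d²/Var(age). Here p is the proportion in one group and d the difference in mean age between the groups. For even ages Var(age) = (6² − 1)/12 = 2.917, and d = 3 for every cut.

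- Central cut (8–10 v 11–13): 0.25 × 9 / 2.917 = 0.771.
- One year off centre (8–9 v 10–13, or 8–11 v 12–13): (1/3)(2/3) × 9 / 2.917 = 0.686.
- Extreme cut (8 v 9–13, or 8–12 v 13): (1/6)(5/6) × 9 / 2.917 = 0.429.

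**Step 2: approximate power.** Fisher z gives power = Φ(atanh(r)√(n−3) − 1.96). With n = 21 and r = 0.5, age in years gives Φ(0.549 × 4.243 − 1.96) = Φ(0.37) = 64%. With the central split, r becomes 0.5 × √0.771 = 0.439, giving Φ(0.471 × 4.243 − 1.96) = Φ(0.04) = 52%.

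**Step 3: simulated power with the discrete score.** 40,000 replicates per scenario; tie-corrected Mann-Whitney without continuity correction; Spearman t-test.

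| True pattern | Spearman, age in years | Central cut | One year off | Extreme cut |
|---|---|---|---|---|
| Linear, r = 0.5 | 62% | 49% | 44% | 26% |
| Linear, r = 0.3 | 24% | 19% | 17–18% | 11% |
| Step of 1.2 SD at age 11 | 53% | 66% | 35% | 13% |
| No age effect (type I error) | 5.1% | 4.8% | 4.8–4.9% | 4.2% |

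For a linear trend with r = 0.5, the gain from using age in years is therefore 62 − 49 = 13 points against a central cut, 62 − 44 = 18 one year off and 62 − 26 = 36 at an extreme cut. At r = 0.3 the gains are 5, about 6 to 7, and 13 points. For a step exactly at the cut, Spearman loses 66 − 53 = 13 points.

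**Step 4: sensitivity at r = 0.5, central cut v Spearman.** Near-continuous total score 52% v 64%; top-heavy scores 45% v 56%; ages clustered at both ends 54% v 62%; 18 surveys 42% v 54%; 15 surveys 35% v 46%. The direction is the same throughout, with gains of 8 to 12 points.

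**Step 5: what 21 children can show.** An observed Spearman correlation of 0.3 has standard error √((1 + 0.3²/2)/18) = 0.241 on the Fisher scale. The limits are 0.310 ± 1.96 × 0.241, which transform back to −0.16 and 0.65.

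**The case against.** The strongest reply is that the real gap is one of reporting: name the cut-point and group sizes and the comparison becomes reproducible. On this view, changing the method is a preference. The documents give no shape that favours a linear trend any more than a step. Mann-Whitney does better when the change falls at or near the cut: 66% v 53% for the step, 53% v 50% for a rise over about three years centred on it, and 49% v 30% for one non-monotone pattern. The test is also described as already done, so power cannot alter it, and a new analysis is a second look at the same scores.

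Much of this stands. The power advantage is conditional on shape, and the new analysis must be labelled post hoc. But the advantage of the split depends on the cut lying close to the change: one year off the step, Mann-Whitney falls to 35% against 53% for Spearman. With no age hypothesis stated, age in years is the more natural default. It also removes the dependence on a boundary that the reader cannot see.

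Three stronger readings are tempting and are not supported:

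- **That the test is invalid.** A single cut fixed in advance holds its type I error at about 4% to 5%.
- **That the boundary was chosen after looking at the scores, or that several were tried.** The text is silent on how the groups were formed, and silence is not evidence of selection.
- **That age in years is always better.** The step result shows otherwise.

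**Conclusion.** The point holds as a modest improvement in method. The age groups are undefined, and reducing ages 8 to 13 to two groups costs power when satisfaction changes roughly linearly with age. Because the cut is unknown, the cost has to be given as a range: about 13 to 36 points at r = 0.5 and about 5 to 13 points at r = 0.3, depending on where the cut lies. These figures rest on the assumed 21 surveys, even ages and 5-point score. That only VR children answered the survey is itself inferred.

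The consequence is small. Satisfaction is a listed outcome, but its comparison by age is not. At r = 0.3 neither method exceeds about 24% power, so a null result would mainly reflect the sample size. A reader might infer that the trial's main findings are weakened; they are not, because no pain, mobility or PedsQL comparison uses these age groups.

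**What to change.** Make satisfaction against age in years the reported age analysis, using Spearman correlation with a 95% confidence interval or proportional-odds regression on age. Label it exploratory and post hoc, since the text says the age-group test has already been applied.

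Keep the existing age-group comparison as descriptive, stating the cut-point, the number of children in each group and whether the cut was set before the scores were seen. Do not claim that there is no age effect; let the confidence interval show how little 21 children can exclude.

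The downside should be stated alongside. Spearman assumes a monotone trend and can miss a change concentrated at one age or one that reverses. A plot of satisfaction by year of age would let readers judge this.

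The cost is a few sentences in the statistics section or report. No new data are needed if age in years is on file (assumed), and SPSS, the software named in the plan, offers both methods.
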